6. ASSESSMENT AND FOLLOW-UP

There will be no follow-up after the study has completed. The end of study definition is last subject last visit.

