BMI	Body mass index

KEYWORDS

COX-2, prostacyclin, ibuprofen, Vioxx, thrombosis, nitric oxide, ADMA, L-arginine

STUDY SUMMARY

TITLE COX-2/prostacyclin/ADMA/NO axis in the cardiovascular system

DESIGN Two arm, single centre mechanistic study. Subjects will be computer randomised to either arm.

AIMS

- To perform a systemic analysis of how COX-2 inhibition by celecoxib affects vascular function and 'omic biomarkers including those associated with the COX-2/prostacyclin/ADMA axis in healthy male volunteers
- To investigate how this is altered by L-arginine supplementation

OUTCOME MEASURES

Primary endpoint: endothelial function measured using EndoPAT

Secondary endpoints: Blood pressure, cardiovascular biomarkers, eicosanoid and methylarginine/amine levels, plasma proteome and blood transcriptome

POPULATION Healthy male volunteers

ELIGIBILITY

Inclusion Criteria	Exclusion Criteria

 • Male, 18-40 years old • No abnormal findings on medical history, screening, physical examination, haematology, biochemistry, urinalysis and vital signs (sitting blood pressure, resting pulse rate, respiratory rate and body temperature within two weeks of commencement date) • Normal fasting lipid profile (Soverson et al, 1994) • Non-smoking • Clear venous access in upper limbs • BMI 18-30 • No history or signs of drug abuse • No other medication 4 weeks before or during study • Informed written consent 	
 • Any history of allergy to NSAIDs or arginine • Significant medical conditions • Pulse rate<50 beats/minute • Sitting systolic blood pressure <80 or >160 mmHg • Sitting diastolic blood pressure <60 or >100 mmHg • Baseline endothelial dysfunction (as defined by EndoPAT; LnRHI<0.51) • Participation in other clinical study 8 weeks before or during study • Donation of blood 8 weeks before or during study • COVID-19 vaccination within 4 weeks • Positive COVID-19 test

TREATMENT

[figure not shown]
Celecoxib: 200 mg b.i.d (400mg total/day)

L-arginine 5g b.i.d. (10g total/day)

Celecoxib, L-arginine or placebo will be dispensed against an individual prescription by a registered pharmacist. Drugs will be stored at the Imperial/NIHR Clinical Research Facility. Drugs or placebo will be administered orally.

DURATION 7 days of active treatment in each study arm (see flowchart below)

STUDY FLOWCHART AND TIMELINE

Exam	Visit number	1	2	3	4
	0 (Screening)				
Informed consent	x				
Medical history	x				

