Physical exam/questionnaire	x				
Blood pressure	x	x	x	x	x
Heart rate	x	x	x	x	x
Breathing rate	x				
Temperature	x				
Height	x				
Weight	x				
Urine sample	x	x	x	x	x
Blood sample 50ml	x	x	x	x	x
EndoPat	x	x	x	x	x
Study medication(s) dispensed		x		x	

ANALYSIS/STORAGE OF SAMPLES

Samples will be stored in freezers or refrigerators or other appropriate place within secure, swipe access only facilities at Imperial College London. Results obtained during the study which will be stored on University Computers (including University Laptops) in a pseudonymised format; as part of our study we will measure gene expression and a large number of different proteins and other mediators in the volunteer's blood. Under GDPR (Recital 34) the gene expression data that we measure is classified as 'identifiable personal data'. However, the type of analysis that we are performing involves RNA and not genomic DNA which means that it would not be possible for a 'motivated individual with no special skill in genetics and no access to non-public datasets' to be able to identify individuals. Furthermore, we have performed a data-protection risk assessment on this study.

We will also send samples for analysis to collaborators within and outside of the EEA. All samples and data will be coded before leaving the study team. For some measurements the samples will be sent to service providers under contracts and for others to academic collaborators. All samples would be pseudonymised before leaving the study team and analysis conducted either done under contract for payment and/or as part of an academic collaboration. Where required a transfer agreement will be in place. Samples will be stored for future use subject to any requirement for future ethical approval.

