3. STUDY DESIGN

Two arm, single centre mechanistic study.

Forty healthy male volunteers, twenty in each arm.

Primary endpoint: Endothelial function measured using EndoPAT

Secondary endpoints: Sitting blood pressure, cardiovascular biomarkers, eicosanoid and methylarginine/amine levels, plasma proteome and blood transcriptome.

Functional Endpoints	Biomarkers

 • EndoPAT- endothelial function • Blood pressure 	
 • Methylarginines- ADMA, SDMA and L-NMMA • Amino acids- full range including L-arginine, L-ornithine, L-citrulline. • Eicosanoids- full range including prostacyclin and PGI-M • Cardiovascular Biomarkers- thromboxane, endothelin-1, nitric oxide, renin, angiotensin, apolipoproteins, D-dimer, Sicam-1 and CRP • Renal biomarkers- creatinine, urea, cystatin C, KIM-1 and albumin

Healthy male volunteers will be randomized to 7 days' treatment with celecoxib (200mg b.i.d.; the standard maximum anti-inflammatory dose) or placebo in a double blinded format. Samples and measurements will be made at baseline and after the final dose. Following a washout of at least 4 weeks, L-arginine (Lambers Healthcare Limited) may be administered in a dose of 5g b.i.d. (10g total/day) as per the study flowchart (page 5). A rational approach was taken in selecting the arginine dose since 10g/day increases plasma arginine by $\approx 40\%$ ¹⁷. At each visit, the primary endpoint will be endothelial function, measured using EndoPAT, which measures changes in flow-mediated endothelial function in the microvasculature. Importantly, EndoPAT is clinically validated with scores that correlate with cardiovascular risk¹⁸. Additionally, at each study visit, blood pressure, cardiovascular biomarkers (by ELISA) and

eicosanoid and methylarginine/amine levels (by GC/LCMS/MS) will be measured. Samples will also be collected for measurement of 'omic' biomarkers including transcriptomics, proteomics, lipidomics and metabolomics. Additionally volunteers will monitor and record their blood pressure readings daily using a home monitoring device and protocols validated and suggested (respectively) by the British and Irish Hypertension Society. In vivo aspects of this study will be performed using validated protocols¹⁵ and using facilities and staff at the NIHR/Wellcome Trust Imperial College Clinical Research Facility.

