Once participants are enrolled and randomised in the study, the study visits (visits 1 & 2 in phase 1 and visits 3 & 4 in phase 2) need to occur exactly 7 days apart. If participant attends visit 1 but is unable to attend visit 2 for a reason that is unrelated to the study medication e.g. develops an unrelated illness or cannot attend for personal reasons, the participant will have the option to re-enrol as a new participant if there is at least a 4-week washout period if they wish to do so. These participants will need to re-attend screening and re-consent and will be treated as a new participant with a new study number. To avoid double counting, any data obtained from the initial enrolment will not be used and will be superseded by the data generated by re-enrolment.

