5. ADVERSE EVENTS

Definitions

Adverse Event (AE): any untoward medical occurrence in a clinical study subject.

Serious Adverse Event (SAE): any untoward and unexpected medical occurrence or effect that:

- **Results in death**
- **Is life-threatening** – *refers to an event in which the subject was at risk of death at the time of the event; it does not refer to an event which hypothetically might have caused death if it were more severe*
- **Requires hospitalisation**
- **Results in persistent or significant disability or incapacity**
- **Is a congenital anomaly or birth defect**

Medical judgement will be exercised in deciding whether an AE is serious in other situations. Important AEs that are not immediately life-threatening or do not result in death or hospitalisation but may jeopardise the subject or may require intervention to prevent one of the other outcomes listed in the definition above, will also be considered serious.

Reporting procedures

All adverse events will be reported. Depending on the nature of the event the reporting procedures below will be followed. Any questions concerning adverse event reporting will be directed to the Chief Investigator ([name]) and the medically qualified Investigators ([name] and [name]) in the first instance.

Non serious AEs

All such events, whether expected or not, will be recorded.

Serious AEs

A SAE form will be completed and sent to the medically qualified Investigator, [name], within 24 hours. However, relapse and death and hospitalisations for elective treatment of a pre-existing condition do not need reporting as SAEs.

All SAEs will be reported to the Imperial College Research Ethics Committee where in the opinion of the Chief Investigator, the event was:

- 'related', i.e. resulted from the administration of any of the research procedures; and
- 'unexpected', i.e. an event that is not listed in the protocol as an expected occurrence

Reports of related and unexpected SAEs will be submitted within 15 days of the chief investigator/medically qualified investigator becoming aware of the event, using the NRES SAE form for non-IMP studies. The Chief Investigator will also notify the Sponsor of all SAEs.

Contact details for reporting SAEs

[contact]

CI email: [contact]

Please send SAE forms to: [name]

[contact]

[contact] (Mon to Fri 09.00 – 17.00)

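### No adverse-event enquiry is scheduled after the last dose, so events starting after visit 4 reach the study only if the volunteer reports them unprompted

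*Combined protocol and SAP*

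**What the plan says.** Section 6 of the combined protocol and SAP reads: "There will be no follow-up after the study has completed. The end of study definition is last subject last visit".

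The timing of the final visit follows from four other places:

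- Study Summary, Duration: "7 days of active treatment in each study arm".
- Section 4, Re-enrolment: "visits 1 & 2 in phase 1 and visits 3 & 4 in phase 2) need to occur exactly 7 days apart".
- Section 3: "Samples and measurements will be made at baseline and after the final dose".
- Study flowchart: visit 4 is the last column. The row "Study medication(s) dispensed" is marked at visits 1 and 3 only. There is no row for adverse events.

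Between the phases, section 3 says: "Following a washout of at least 4 weeks, L-arginine (Lambers Healthcare Limited) may be administered". Section 7 allows the interim analysis, held during that washout, to decide whether the L-arginine part goes ahead.

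On recording, section 5 says "All adverse events will be reported" and, for non-serious events, "All such events, whether expected or not, will be recorded". It gives no start date, stop date or post-dose period for collection, and does not say when participants are to be asked.

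**The concern.** Section 5 sets a complete-capture standard. Section 6 leaves no occasion after the last exposure on which anyone would ask. An event that begins on the evening of visit 4, or during the following week, comes to light only if the man gets in touch on his own initiative. For the last man in the study, the study has by definition already ended. If phase 2 is not started, visit 2 becomes the final visit and phase 1 has the same gap.

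What is at stake is the safety record. These are healthy volunteers with nothing to gain clinically. The background in section 1.1 itself describes class-wide cardiovascular warnings for NSAIDs, and a risk that appears within 1-2 weeks of use. A table of adverse events from this study would be hard to interpret if the reader cannot tell over what period events were sought, or whether they were sought at all.

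**Working it through.** The plan gives no figure on this point, so there is none to reproduce. The check is a day-count from the visit schedule, followed by an illustration under stated assumptions.

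**Inputs from the documents.** Treatment lasts 7 days per phase (Study Summary). Visits 1-2 and 3-4 are 7 days apart (section 4). End-of-phase measurements follow the final dose (section 3). The washout is at least 4 weeks, or 28 days (section 3). Nothing is scheduled after visit 4 (flowchart, section 6). There are 20 men per arm, 40 in all (section 3).

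**Step 1: scheduled time after the last dose.** Formula: day of next scheduled contact after the end-of-phase visit, minus day dosing ends, counting from the first visit of the phase.

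| Situation | Dosing ends | Next scheduled contact | Scheduled post-dose time |
|---|---|---|---|
| Phase 1, man continues | day 7 | visit 3, day 7 + 28 = 35 or later | 35 - 7 = at least 28 days |
| Phase 1, phase 2 not started | day 7 | none after visit 2 | 0 days |
| Phase 2 | day 7 | none after visit 4 | 0 days |

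The 28 days in the first row are only time to the next contact. No call or visit falls within the washout, and the flowchart lists no adverse-event enquiry at visit 3. Visit 3 is a chance to mention an event, not planned capture.

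**Step 2: does this reach any planned comparison?** The on-treatment windows are equal: 7 days in phase 1 and 7 days in phase 2. Within a phase both arms follow the same schedule, so the gap is the same in each arm. If a common post-dose period of w days is added, both phases have 7 + w days and remain equal for any w.

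**Step 3: how many events could be involved?** The documents give no rates. Assume that a fraction r of men, 5% to 20%, has a drug-related event, and that a fraction f of those events, 10% to 50%, starts after the last dose. The expected number starting after the final contact is N x r x f.

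- N = 20: from 20 x 0.05 x 0.10 = 0.1 to 20 x 0.20 x 0.50 = 2.0.
- N = 40: from 40 x 0.05 x 0.10 = 0.2 to 40 x 0.20 x 0.50 = 4.0.

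These are events that would depend on an unsolicited report. They are not events known to be lost.

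**Step 4: sections 5 and 6 side by side.** Section 5 requires every event to be recorded and sets no cut-off. Section 6 ends contact with each man at the visit where dosing ends. The two can both be followed literally, but together they give no means of meeting section 5 for events that start after the last exposure.

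**The case against.** The best case for the plan has several parts.

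- Section 5 has no cut-off date. Because study end is defined for the whole study, men who finish early can still report while others are in follow-through. This stands, but it describes passive reporting, and it gives nothing to the last man.
- Section 4 provides that study-visit results needing further follow-up are passed to the participant's general practitioner, and blood and urine are taken at visit 4. This stands for abnormal results. It does not cover symptoms that begin after the visit.
- Section 4 describes celecoxib as relatively safe and L-arginine as well tolerated. That is a reason for light follow-up. It does not explain an undefined collection window.
- Participant-facing pages are not among the documents available, so instructions to report later events may exist. If so, the report would still have to come from the participant.

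A reader might also infer that the phases cannot be compared for safety, or that the L-arginine phase would look safer because a phase 1 event has at least 35 days to be heard and a phase 2 event only 7. The documents do not support this. The ratio of 5 to 1 (35/7) arises only if every washout event is credited to phase 1, and nothing in the plan says so. The on-treatment windows are 7 days in each phase. Section 2 judges L-arginine on functional endpoints and biomarkers. Section 3 lists no safety endpoint, and section 7 plans no adverse-event comparison between phases.

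**Conclusion.** The point holds as a gap in safety capture. Visit 4 is the last scheduled contact and falls at the end of dosing, leaving 0 scheduled days after the second exposure, and 0 after the first if phase 2 does not proceed. Events starting afterwards are at risk of being missed. Beneath this lies a plan-wide omission: no collection window and no adverse-event enquiry in the flowchart.

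It would go too far to say that toxicity is in fact under-recorded. The text requires all events to be recorded and does not bar late reports, so this is a risk and not a finding. The primary EndoPAT analysis, the biomarker analyses and the between-arm comparison within each phase are unaffected.

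The day-count rests on the visit spacing and on section 6 alone. The treatment figure is not shown, but the phase 2 regimen does not change the count. The range of 0.1 to 2.0 events per 20 men rests wholly on the assumed r and f. The change is worth making because it is cheap and concerns healthy volunteers.

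**What to change.** Reconcile sections 5 and 6 as follows.

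1. In section 6, replace the statement that there is no follow-up with one remote adverse-event enquiry, by telephone or email, at a fixed interval after each man's last dose in each phase. Include the men whose last dose precedes visit 2 when phase 2 does not go ahead. The interval is for the sponsor to choose.
2. In section 5, define one collection window, from first dose to that enquiry, identical in both phases.
3. Add the enquiry to the flowchart.
4. Define end of study as the last such contact.

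The cost is one short call or email per man per phase by existing staff (at most 40 x 2 = 80 contacts for the planned 40 men), an added flowchart entry and a slightly later study end. No dose, endpoint or sample size changes.

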7. STATISTICS AND DATA ANALYSIS

Sample size: This is a novel mechanistic study where the primary endpoint is the effect of celecoxib on endothelial function measured using the EndoPAT device. We anticipate that we will require n=20-40 in each study arm to detect a difference based on previous work using similar drugs and alternative measurement approaches. For example Carlsson and Wennmalm (1983)¹⁹ showed a reduction in endothelial function with ibuprofen (effect size: 0.80 standard deviations) and diclofenac (effect size: 1.06 standard deviations). This equates to a power of 72-92% at n=20 and 95-100% at n=40 to detect a difference between groups at a nominal significance threshold of p<0.05. As we are using a different drug and an alternative measurement platform, power can only be estimated broadly. As such, we will perform an interim analysis of data after studying n=20 volunteers per group during the 'wash out' period. At this point, actual effect size and variance will be determined and experimental power re-calculated. If our primary endpoint is not achieved, we may revise our endpoints and/or if additional power is required, we will reserve the option to recruit up to an additional n=20 volunteers per group. Dependent upon the results the interim analysis may also serve as a stop-go checkpoint for continuation of the L-arginine arm of the study.

Data analysis: Data will be analysed according to approaches applicable to the measurement. This includes standard parametric and non-parametric tools (including Fisher's exact tests, Student's t-tests, 1-way and 2-way ANOVAs, Mann Whitney U-tests and Kruskall-Wallis tests) as well as specialised tests for large omic data sets (including modified t-test with false discovery correction where appropriate). Across all tests differences will be considered significant where p<0.05.

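### Section 7 lets the endpoints be revised once EndoPAT has failed at the interim, with no safeguards; if the primary is replaced and there is no true effect, the chance of a false primary success exceeds 5%

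*Combined protocol and SAP*

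**What the plan says.** Section 7 (Sample size) states that "the primary endpoint is the effect of celecoxib on endothelial function measured using the EndoPAT device". It continues: "we will perform an interim analysis of data after studying n=20 volunteers per group". Section 3 plans twenty volunteers in each arm, so this interim falls at the full base sample size. At that point "actual effect size and variance will be determined and experimental power re-calculated". An observed effect size requires celecoxib to be compared with placebo, so this is a comparative look and not a blinded check of variance.

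The consequence follows: "If our primary endpoint is not achieved, we may revise our endpoints". The same sentence adds, as an alternative or in combination, that "we will reserve the option to recruit up to an additional n=20 volunteers per group".

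On error control, Section 7 (Data analysis) says: "Across all tests differences will be considered significant where p<0.05". The only multiplicity control is in the phrase "specialised tests for large omic data sets (including modified t-test with false discovery correction where appropriate".

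Section 3 shows what could be promoted: "Secondary endpoints: Sitting blood pressure, cardiovascular biomarkers, eicosanoid and methylarginine/amine levels, plasma proteome and blood transcriptome".

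**The concern.** The trigger for revising the endpoints is the trial's own result on the primary. The plan does not define what counts as not achieved. It lists no replacement and gives no rule for choosing one. It does not say whether a revised endpoint would be tested on the same volunteers, on pooled data or on new volunteers only, and it does not adjust the significance level. False discovery correction might be read to cover the broad eicosanoid and amino acid panels, but it does not reach blood pressure, and nothing says it would apply to a promoted primary. The documents do not say which biomarker results will exist at the interim. By then, however, blood pressure will have been measured and samples taken at visits 1 and 2.

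Two things are at stake. With no true effect, a switch gives the trial a second chance to declare primary success, and more chances if the best-looking candidate is picked. With a true effect on the replacement, the declared primary result may be correct but answer a different question from the hypothesis in Section 1.2, which is about endothelial function.

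**Working it through.** **1. The plan's own power figure.** Inputs from Section 7: effects of 0.80 and 1.06 SD, 20 or 40 per group, p<0.05. Sidedness is not stated; two-sided reproduces the figures. Normal approximation: power = Φ(d√(n/2) − 1.96).

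- n=20: Φ(2.530 − 1.96) = 71.6%; Φ(3.352 − 1.96) = 91.8%. Stated: 72-92%.
- n=40: Φ(3.578 − 1.96) = 94.7%; Φ(4.741 − 1.96) = 99.7%. Stated: 95-100%.

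The stated power is reproduced. It is specific to effect sizes proposed for endothelial function, so it does not carry over to a replacement endpoint.

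**2. Assumptions for the error rate.** The documents do not give the number of candidates k, the correlation rho among EndoPAT and the candidates, or how often a switch would occur. I take k = 1 to 10, rho = 0 to 0.8, no true effect on any endpoint, a switch whenever EndoPAT fails, and the candidate with the largest interim statistic chosen. EndoPAT is tested once, at the interim, so the rate with no switch is 5%.

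**3. Closed forms.**

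- Same 20 per group, independent endpoints: 1 − 0.95^(k+1). For k = 1, 2, 5 and 10 this is 9.75%, 14.3%, 26.5% and 43.1%.
- New volunteers only, each test at 0.05: 1 − 0.95² = 9.75% for any k, because the choice made on the first stage does not affect independent new data.

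**4. Simulation with correlated endpoints.** 400,000 null trials per setting, two-sided tests at 1.96. Trial-level chance that either EndoPAT or its replacement is declared a primary success:

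| Data used for the replacement | rho | k=1 | k=2 | k=5 | k=10 |
|---|---|---|---|---|---|
| Same 20 per group | 0 | 9.7% | 14.2% | 26.5% | 43.1% |
| | 0.5 | 9.1% | 12.5% | 20.7% | 30.3% |
| | 0.8 | 7.8% | 9.8% | 13.8% | 18.0% |
| Pooled, 20+20 per group | 0 | 9.7% | 12.7% | 18.9% | 25.2% |
| | 0.5 | 9.5% | 11.9% | 16.4% | 20.6% |
| | 0.8 | 8.8% | 10.5% | 13.0% | 15.0% |

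A check with Student t statistics (k = 1 and 5, rho = 0 and 0.8) gave 7.8-26.6% on the same data and 8.9-18.6% pooled. Even at rho = 0.95 the same-data figures are 6.4% (k=1), 8.9% (k=5) and 10.3% (k=10).

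**5. Switching less often.** If only half of the failed trials switch, the excess over 5% halves. The lowest same-data cell becomes 5 + (7.8 − 5)/2 = 6.4% and the highest 5 + (43.1 − 5)/2 = 24.1%. New volunteers only gives 5 + 4.75/2 = 7.4%.

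**6. The replacement's own error, given that EndoPAT failed.** This is (trial-level rate − 5%)/95%.

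- One candidate, same data: (7.8 − 5)/95 = 2.9% at rho 0.8, and (9.75 − 5)/95 = 5.0% at rho 0.
- Best of five, same data: about 9% to 23% over rho 0 to 0.8, but (8.9 − 5)/95 = 4.1% at rho 0.95.
- New volunteers only: 5.0%.

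**The case against.** The text says may, and speaks of endpoints in the plural. It could refer to secondary measures, or to the L-arginine phase or new volunteers only. The study is mechanistic, the threshold is called nominal, and the option is openly declared. All of this is fair, and it is why the point is conditional on the primary actually being replaced. It does not remove the point: nothing in the available text limits the option to the harmless readings, and confining the replacement to new volunteers still gives 9.75% when both tests are at 0.05.

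The objection about baseline also stands in part. If EndoPAT itself were kept, extended to 40 per group after every non-significant interim and re-tested on pooled data at 0.05, the error would be about 8.3% with no switch at all. The pooled and new-volunteer figures are therefore not a net cost of switching over a trial that would have extended anyway.

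A reader might infer more than the documents support:

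- That the plan intends to search many markers and promote the best. It states no selection rule, so this is permitted but not planned. The 43% figure needs ten independent candidates, a switch every time and the best always taken; related markers lie nearer the bottom of the ranges.
- That any replacement's own test would exceed 5%. With one pre-named candidate, or new volunteers only, it is about 5% or less. Taking the best of five on the same data exceeds 5% for correlations up to 0.8, but not at 0.95.
- That a positive result on a promoted marker would be false. Section 1.1 describes COX-2 as acting through prostacyclin, and Section 3 lists prostacyclin among the measures. A change there could well be real, and the error rates above would not apply.

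**Conclusion.** The concern holds in conditional form. Section 7 allows the primary to be replaced after its comparative result is known, without the usual safeguards. If that happens and celecoxib has no true effect on EndoPAT or the candidates, the trial-level chance of a false primary success exceeds 5% for any replacement not perfectly correlated with EndoPAT. The direction is firm. The size depends on the assumed number of candidates, their correlation and the frequency of switching, none of which the documents give.

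If the replacement is truly affected by COX-2 inhibition, the fault is different: a genuine positive would be presented as the primary result without testing whether endothelial function is compromised, and without a power calculation behind it. The mechanistic setting lessens the consequences, but the plan names a primary endpoint, powers for it and sets a threshold, so the clause should be changed before any interim comparison is seen.

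**What to change.** Replace the sentence in Section 7 that offers endpoint revision with wording such as:

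> If the primary endpoint is not achieved and more power is needed, recruitment may be extended by up to 20 volunteers per group. The EndoPAT comparison of celecoxib with placebo remains the primary endpoint whatever the interim shows. Any endpoint promoted to primary, or newly chosen, after the interim is reported as exploratory.

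This changes no visits, samples or sample size and loses no power for EndoPAT. The pre-listed secondary endpoints keep their status and can all be analysed and reported. The cost is that the sponsor can no longer relabel a secondary result as primary, even one tested only in new volunteers. If EndoPAT proves insensitive to celecoxib, the primary result stays negative.

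The change closes the endpoint-switching route only. The unadjusted extension of EndoPAT from 20 to 40 per group is a separate matter and needs its own correction.

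### EndoPAT can be tested at 20 per group and again after adding up to 20 per group, each time at p<0.05, so its false-positive rate can reach 8.3% to 8.7% instead of 5%

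*Combined protocol and SAP*

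**What the plan says.** Section 3 plans forty volunteers, twenty per arm. Section 7 (Sample size) then says "we will perform an interim analysis of data after studying n=20 volunteers per group", so the interim falls at the full planned size. The look is comparative: "At this point, actual effect size and variance will be determined and experimental power re-calculated".

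Two consequences may follow, separately or together. One is "If our primary endpoint is not achieved, we may revise our endpoints". The other is "if additional power is required, we will reserve the option to recruit up to an additional n=20 volunteers per group". The interim may also decide whether the L-arginine part continues.

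The threshold is in Section 7 (Data analysis): "Across all tests differences will be considered significant where p<0.05". The only multiplicity correction named is false discovery control for the omic data. There is no alpha split, stopping boundary or combination test, and no rule for when or by how much to extend.

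The power statement is "This equates to a power of 72-92% at n=20 and 95-100% at n=40 to detect a difference between groups", for effects of 0.80 and 1.06 SD.

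The EndoPAT analysis is not pinned down. Section 3 says "At each visit, the primary endpoint will be endothelial function, measured using EndoPAT". LnRHI appears only as an eligibility cut-off. On methods, Section 7 says "This includes standard parametric and non-parametric tools" and lists several without assigning one to EndoPAT.

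**The concern.** The wording that the endpoint was not achieved implies that p<0.05 at 20 per group counts as success. Recruiting for more power implies a further test. Together these give the primary endpoint two chances at 0.05, the second taken only when the first fails, so the overall error exceeds 5% whenever extension can occur.

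A celecoxib effect on EndoPAT could then be declared with a false-positive rate up to about 1.7 times nominal (8.65/5 = 1.73). The stated powers take no account of this, because they assume one unadjusted look.

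The open choice of variable and test, and the freedom to revise endpoints after the by-arm look, add further inflation that the documents do not allow anyone to quantify. None of these choices can be pre-specified once the interim data have been seen by arm.

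**Working it through.** **Inputs.** From Section 7: threshold 0.05, interim at 20 per group, extension of m = 0 to 20 per group, effects d = 0.80 and 1.06 SD. From Section 3: two arms of twenty.

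**Step 1: reproduce the plan's power and infer sidedness.** The plan does not say whether tests are one- or two-sided. The normal approximation is power = Φ(d√(n/2) − c), with c = 1.960 (two-sided) or 1.645 (one-sided). For example, at d = 0.80 and n = 20, two-sided: Φ(2.530 − 1.960) = Φ(0.570) = 71.6%.

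| n per group | Two-sided, 0.80 / 1.06 SD | One-sided, 0.80 / 1.06 SD | Plan |
|---|---|---|---|
| 20 | 71.6% / 91.8% | 81.2% / 95.6% | 72-92% |
| 40 | 94.7% / 99.7% | 97.3% / 99.9% | 95-100% |

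Only two-sided testing reproduces the plan. The exact two-sample t-test gives slightly less: 69.3% / 90.4% at 20 and 94.2% / 99.7% at 40.

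**Step 2: type I error with two looks at 0.05.** Let z1 be the interim statistic and z2 the statistic from the new volunteers alone. The pooled statistic is (√20·z1 + √m·z2)/√(20+m). Given z1, the chance under the null that the pooled test rejects is

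CE(z1, m) = 1 − Φ[(1.96√(20+m) − √20·z1)/√m] + Φ[(−1.96√(20+m) − √20·z1)/√m].

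The overall error is 0.05 plus the integral of CE(z1, m)·φ(z1) over those values with |z1| < 1.96 at which the trial is extended.

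| Rule after a non-significant interim | Type I error |
|---|---|
| No extension, or a single test | 5.0% |
| Always add 5 / 10 / 15 per group | 7.1% / 7.7% / 8.1% |
| Always add 20 | 8.3% |
| Add 20 only if interim p<0.1 / p<0.2 | 5.8% / 6.8% |
| Add 20 only if conditional power ≥50% / ≥70% / ≥80% | 6.5% / 5.8% / 5.4% |
| Size 1-20 chosen from z1 to maximise rejection | 8.65% |

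Conditional power here is for the pooled test at 40 per group, at the observed effect: 1 − Φ(1.96√2 − 2|z1|). It reaches 87.5% at |z1| = 1.96, so the 80% rule can trigger.

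A simulation of 1,000,000 null trials with t-tests gave 8.33% (always add 20), 6.79% (p<0.2) and 5.82% (p<0.1).

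**Step 3: thresholds that hold 5%.** For looks at 20 and 40 per group the correlation is √0.5.

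- The same critical value at both looks is 2.178, that is p<0.0294 (overall 5.00%; simulation 5.01%).
- A stricter first look uses critical values 2.797 and 1.977, that is p<0.0052 then p<0.048 (overall 5.00%).
- The combination Z = (z1 + z2)/√2 has fixed weights, and under the null z1 and z2 stay independent standard normal whatever m is chosen. At p<0.0294 it gives 4.98-5.00% for fixed extensions of 5 to 20, and 4.98-4.99% under two illustrative rules that choose m from the interim.

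**Step 4: power for 0.80 / 1.06 SD** (noncentral t at 20 per group; 300,000 simulations each with extension).

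| Design | At 20 per group | With extension |
|---|---|---|
| 0.0294 twice, 20 more | 60.7% / 85.7% | 92.0% / 99.4% |
| 0.0052 then 0.048, 20 more | 34.7% / 65.0% | 94.1% / 99.7% |
| Combination at 0.0294, 10 more | 60.7% / 85.7% | 82.8% / 97.2% |
| Combination at 0.0294, 20 more | 60.7% / 85.7% | 91.8% / 99.4% |

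**The case against.** The plan only reserves the option to extend, and 8.3% requires every non-significant interim to be extended in full, even one pointing the wrong way. If the trial is extended by 20 only when the interim points in the hypothesised direction, the figure is 6.7%. Recalculated power could also mean ordinary power at 40 per group from the observed effect. After a non-significant interim that peaks at Φ(1.96√2 − 1.96) = 79.2%, so an 80% requirement would never trigger extension and the error would stay at 5.0%; a 72% requirement gives 5.4%. The 8.65% figure needs a size chosen to maximise rejection, which the plan does not suggest. The retest is inferred, and this is a mechanistic study in healthy volunteers.

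Much of this stands as a limit on the size. The 5.4% to 6.8% range illustrates named rules. Other restricted rules with 20 more per group run from 5.0% to just under 8.3% (interim p<0.5 gives 7.8%). It does not remove the defect: the plan states none of these rules, so the error rate depends on a decision made after the data are seen. A mechanistic aim is no exemption when the plan sets a primary endpoint, a power claim and a significance threshold.

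It is also fair that Section 7 fixes the contrast as celecoxib against placebo. The EndoPAT metric, the handling of baseline and the test remain open.

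**Conclusion.** The concern holds and must be fixed before the interim data are seen by arm. As written, the type I error for EndoPAT is 8.3% if a non-significant interim always adds 20 per group, 5.4% to 6.8% under the restricted rules tabulated, and up to 8.7% if the size is chosen from the interim. It is 5% only with one test or no extension.

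These figures assume two-sided testing (inferred from the plan's powers), one variable, one test, a significant interim counting as success, and one pooled retest at 0.05. One-sided testing at 0.05 would give 8.0% for always adding 20 and at most 8.2% for a chosen size, so the conclusion does not turn on sidedness. Inflation from revising endpoints comes on top and is not included.

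**What to change.** Before the data at 20 per group are seen by arm, add to Section 7:

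> The primary analysis compares the change in LnRHI from visit 1 to visit 2 between celecoxib and placebo by a two-sided two-sample t-test. It is exempt from the general p<0.05 rule. It is significant if p<0.0294 at 20 per group. If it is not significant and the trial is extended, exactly 20 more per group are recruited and all data are tested at p<0.0294 (overall 5.0%). EndoPAT remains the primary endpoint whatever the interim shows; any endpoint revised after the look is exploratory.

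Another single variable and test would serve if named in advance. Bring the Section 3 sentence on the primary endpoint at each visit into line.

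If a flexible extension is wanted, keep the interim at p<0.0294 and replace the pooled retest with Z = (z1 + z2)/√2 at p<0.0294, with weights fixed beforehand, z1 from the first 20 per group and z2 from the new volunteers only. Another option with the same overall alpha is 0.0052 then 0.048 on pooled data, again with exactly 20 more per group.

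Restate power for 0.80-1.06 SD of the tested variable under the chosen design, using the last table.

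**Cost.** This changes wording only and needs no volunteers beyond the reserved 20 per group. With 0.0294, power at 20 per group falls by 8.6 points (69% to 61%) at 0.80 SD and by 4.7 points (90% to 86%) at 1.06 SD. A non-significant interim therefore becomes more likely: 39% instead of 31%, and 14% instead of 10%. With 0.0052 the falls are 34.6 and 25.4 points. The pooled versions give up smaller extensions; the combination test keeps them.
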